6.3 Subject Population(s) for Analysis

The subject population for analysis is an all randomized population obtained through a convenience sample.

7 Safety and Adverse Events

7.1 Definitions

Unanticipated Problems Involving Risk to Subjects or Others

Any incident, experience, or outcome that meets all of the following criteria:

- Unexpected in nature, severity, or frequency (i.e. not described in study-related documents such as the IRB-approved protocol or consent form, the investigators brochure, etc)
- Related or possibly related to participation in the research (i.e. possibly related means there is a reasonable possibility that the incident experience, or outcome may have been caused by the procedures involved in the research,
- Serious (as defined below) “Serious” is different than “severe” as reported in the CTC criteria that applies a grade to the AE.

Adverse Event

An **adverse event** (AE) is any symptom, sign, illness or experience that develops or worsens in severity during the course of the study. Intercurrent illnesses or injuries should be regarded as adverse events. Abnormal results of diagnostic procedures are considered to be adverse events if the abnormality:

- results in study withdrawal
- is associated with a serious adverse event

- is associated with clinical signs or symptoms
- leads to additional treatment or to further diagnostic tests
- is considered by the investigator to be of clinical significance

Serious Adverse Event

Adverse events are classified as serious or non-serious. A **serious adverse event** is any AE that is:

- fatal
- life-threatening
- requires or prolongs hospital stay
- results in persistent or significant disability or incapacity
- a congenital anomaly or birth defect
- an important medical event

Important medical events are those that may not be immediately life threatening, but are clearly of major clinical significance. They may jeopardize the subject, and may require intervention to prevent one of the other serious outcomes noted above. For example, drug overdose or abuse, a seizure that did not result in in-patient hospitalization, or intensive treatment of bronchospasm in an emergency department would typically be considered serious.

All adverse events that do not meet any of the criteria for serious should be regarded as **non-serious adverse events**.

Adverse Event Reporting Period

The study period during which adverse events must be reported is normally defined as the period from the initiation of any study procedures to the end of the study treatment follow-up. For this study, the study treatment follow-up is defined as 30 days following the last administration of study treatment.

Preexisting Condition

A preexisting condition is one that is present at the start of the study. A preexisting condition should be recorded as an adverse event if the frequency, intensity, or the character of the condition worsens during the study period.

General Physical Examination Findings

At screening, any clinically significant abnormality should be recorded as a preexisting condition. At the end of the study, any new clinically significant findings/abnormalities that meet the definition of an adverse event must also be recorded and documented as an adverse event.

Post-study Adverse Event

All unresolved adverse events should be followed by the investigator until the events are resolved, the subject is lost to follow-up, or the adverse event is otherwise explained. At the last scheduled visit, the investigator should instruct each subject to report any subsequent event(s) that the subject, or the subject's personal physician, believes might reasonably be related to participation in this study. The investigator should notify the study sponsor of any death or adverse event occurring at any time after a subject has discontinued or terminated study participation that may reasonably be related to this study. The sponsor should also be notified if the investigator should become aware of the development of cancer or of a congenital anomaly in a subsequently conceived offspring of a subject that has participated in this study.

Abnormal Laboratory Values

A clinical laboratory abnormality should be documented as an adverse event if any one of the following conditions is met:

- The laboratory abnormality is not otherwise refuted by a repeat test to confirm the abnormality
- The abnormality suggests a disease and/or organ toxicity

- The abnormality is of a degree that requires active management; e.g. change of dose, discontinuation of the drug, more frequent follow-up assessments, further diagnostic investigation, etc.

Hospitalization, Prolonged Hospitalization or Surgery

Any adverse event that results in hospitalization or prolonged hospitalization should be documented and reported as a serious adverse event unless specifically instructed otherwise in this protocol. Any condition responsible for surgery should be documented as an adverse event if the condition meets the criteria for an adverse event.

Neither the condition, hospitalization, prolonged hospitalization, nor surgery are reported as an adverse event in the following circumstances:

- Hospitalization or prolonged hospitalization for diagnostic or elective surgical procedures for a preexisting condition. Surgery should **not** be reported as an outcome of an adverse event if the purpose of the surgery was elective or diagnostic and the outcome was uneventful.
- Hospitalization or prolonged hospitalization required to allow efficacy measurement for the study.
- Hospitalization or prolonged hospitalization for therapy of the target disease of the study, unless it is a worsening or increase in frequency of hospital admissions as judged by the clinical investigator.

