3.1 General Design

The general design of the study is a cohort study with 2 arms in which subjects are randomly assigned to one of 2 experimental groups. The expected duration of subject participation is 7 months. The subjects will complete 7 appointments within this 7 months span that includes initial screening, CBCT evaluation of the site, surgical placement of the dental implant, restoration of the dental implant and associated follow-ups at 7 days, 8 weeks, 11 weeks and 24 weeks.

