7.2 Recording of Adverse Events

At each contact with the subject, the investigator must seek information on adverse events by specific questioning and, as appropriate, by examination. Information on all adverse events should be recorded immediately in the source document, and also in the appropriate adverse event module of the case report form (CRF). All clearly related signs, symptoms, and abnormal diagnostic procedures results should be recorded in the source document, though should be grouped under one diagnosis.

All adverse events occurring during the study period must be recorded. The clinical course of each event should be followed until resolution, stabilization, or until it has been determined that the study treatment or participation is not the cause. Serious adverse events that are still ongoing at the end of the study period must be followed up to determine the final outcome. Any serious adverse event that occurs after the study period and is considered to be possibly related to the study treatment or study participation should be recorded and reported immediately.

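### Adverse event reporting closes 30 days after an undefined last treatment, which on the nominal schedule is at least 61 days before the final visit

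*Combined protocol and SAP*

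**What the plan says.** The rules on which events to capture, and until when, are spread over several places in the combined protocol and SAP:

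- **Section 7.1, Adverse Event Reporting Period.** Mandatory reporting starts with the first study procedure and stops when treatment follow-up stops. For this trial, "the study treatment follow-up is defined as 30 days following the last administration of study treatment".
- **Section 7.1, Adverse Event.** The definition covers anything that "develops or worsens in severity during the course of the study".
- **Section 7.1, General Physical Examination Findings.** "At the end of the study, any new clinically significant findings/abnormalities that meet the definition of an adverse event must also be recorded".
- **Section 7.1, Post-study Adverse Event.** The sponsor is to be told of "any death or adverse event occurring at any time after a subject has discontinued or terminated study participation" if it may reasonably be related to the study.
- **Section 7.2.** Subjects are questioned about events at every contact, and "Information on all adverse events should be recorded immediately in the source document". The next paragraph says "All adverse events occurring during the study period must be recorded". For later events it names only one class for immediate recording and reporting: "Any serious adverse event that occurs after the study period and is considered to be possibly related to the study treatment or study participation".

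The schedule in section 3.1 has "associated follow-ups at 7 days, 8 weeks, 11 weeks and 24 weeks". Under sections 5.5 to 5.7, the abutment and provisional crown are delivered at week 8 and the final crown at week 11. Week 24 holds assessments only, after which the subject leaves the study. No section defines study treatment or its last administration, and section 4.5, on administration, is marked not applicable.

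**The concern.** There are two linked faults. First, the end of the reporting period hangs on an event the protocol does not define. Last administration is drug wording; here the candidates are implant surgery, abutment delivery and crown delivery. Second, whichever of these is chosen, the period closes well before subjects leave the study.

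The sentence that makes recording mandatory in section 7.2 uses the term *study period*, which section 7.1 has just tied to the 30-day rule. Other sentences carry no such limit. Two members of staff could therefore handle the same late event differently, each with support in the text. In a trial of 24 subjects, a few events handled inconsistently would visibly change the safety account.

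**Working it through.** The plan gives no closing date of its own to reproduce; it states only the 30-day rule and the visit weeks. The check is calendar arithmetic followed by a comparison of the rules.

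**Inputs.** Surgery is day 0 and a week is 7 days.

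- Abutment and provisional crown (section 5.5): 8 × 7 = day 56.
- Final crown (section 5.6): 11 × 7 = day 77.
- Visit 7 (section 5.7): 24 × 7 = day 168.
- Follow-up after last treatment (section 7.1): 30 days.

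**Formulas.** Close of period = day of last treatment + 30. Gap = 168 − close. Share = gap / 168.

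| Step taken as last treatment | Day | Period closes | Gap to Visit 7 | Share of 168 days |
|---|---|---|---|---|
| Implant surgery | 0 | day 30 | 138 days | 82% |
| Abutment and provisional crown | 56 | day 86 (week 12.3) | 82 days | 49% |
| Final crown | 77 | day 107 (week 15.3) | 61 days | 36% |

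The period would reach Visit 7 only if the last treatment fell on day 168 − 30 = 138 or later. That is 138 − 77 = 61 days after the nominal crown date, and no treatment is scheduled then.

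**Contact in the gap.** No visit is scheduled between day 77 and day 168, which is 91 days. With the crown as anchor, 61 of those 91 days (67%) lie outside the period; with the abutment, 82 of 91 (90%). Visit 7, the next scheduled contact at which such events would be elicited, also lies outside it.

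**One event under each rule.** Take a non-serious event, reasonably related to the study, that starts and resolves around day 130.

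- Reporting period (7.1): not covered, since 130 is later than 107.
- Definition of an adverse event (7.1): covered, because the subject is still in the study.
- End-of-study findings (7.1): probably not covered, because nothing remains to be found at Visit 7.
- General recording sentence (7.2): covered if it is learned of at any contact.
- Mandatory recording sentence (7.2): not covered, if *study period* has its section 7.1 meaning.
- Later-event sentence (7.2): not covered, because the event is not serious.
- Post-study rule (7.1): not covered, because participation has not ended.

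The same event at day 200 would call for notice to the sponsor under the post-study rule. On the rules that depend on a period, the last weeks of participation therefore carry a narrower duty than the time after it.

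**The case against.** The best reply is that section 7.1 has one template sentence out of step and the rest points to Visit 7 as the working boundary. Questioning happens at every contact, section 7.2 has a general recording sentence without a time limit, and the definition runs over the whole study. Section 7.1 also treats events after the last scheduled visit as later ones. The minimum reporting list in section 7.3 (related, unexpected, and serious or involving risk) has no time limit, nor does the rule in section 7.1 that hospitalization makes an event serious. Section 6.2 plans no adverse event analysis, and the Visit 7 endpoint data are collected regardless.

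Much of this stands. It narrows the exposure to non-serious events between visits, plus serious events judged unrelated that do not involve hospitalization. It is also fair that the day-200 comparison sets a recording duty against a notification duty, and holds only on the period-based rules. Nor would the fix add a contact between days 77 and 168; it settles how events learned of at Visit 7 or at an unscheduled contact are handled.

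It does not remove the problem. The 30-day sentence is written specifically for this study, and the mandatory recording duty uses the term it defines. The broader sentences show that the rules disagree; nothing says which prevails.

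**Conclusion.** The concern holds. The reporting period ends at an undefined point and, on the nominal schedule, no later than day 107. At least 61 of the 168 post-operative days fall outside it, or 82 if the abutment is the anchor. These are shares of calendar time, not of events missed.

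The dates rest on three assumptions: final crown delivery is the latest step that could count as treatment, visits fall on their nominal days (no visit windows are given), and six months means the 24 weeks stated in section 5.7. A late crown would shorten the gap. Reading six months as about 182.6 days would lengthen it to 182.6 − 107 = 75.6 days. If the permanent device were regarded as continuing treatment, no closing date could be derived at all.

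The consequence is inconsistent or absent recording of late events of the kinds named above. The primary and secondary analyses are untouched. The change should be made, but the point does not threaten the trial's main result.

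**What to change.** In section 7.1, define the adverse event reporting period as running from the first study procedure through Visit 7 (week 24) or 30 days after the last study treatment, whichever is later. State which step counts as the last study treatment. Use that one period wherever sections 7.1 and 7.2 refer to the study period, including the preexisting-condition rule and the mandatory recording sentence.

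On the nominal schedule the gap becomes 168 − 168 = 0 days, which adds 61 days of reporting to the latest reading of the current text. The 30-day limb would extend the period only if the last treatment came after day 138.

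The cost is a change of wording and slightly more recording. Visit 7 already exists and subjects are already questioned at each contact, so no visit, procedure or endpoint is added. As a separate clerical matter, the study drug wording in the section 7.3 reporting triggers could be aligned with the devices and procedures studied in the same revision.

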7.2 Recording of Adverse Events

At each contact with the subject, the investigator must seek information on adverse events by specific questioning and, as appropriate, by examination. Information on all adverse events should be recorded immediately in the source document, and also in the appropriate adverse event module of the case report form (CRF). All clearly related signs, symptoms, and abnormal diagnostic procedures results should be recorded in the source document, though should be grouped under one diagnosis.

All adverse events occurring during the study period must be recorded. The clinical course of each event should be followed until resolution, stabilization, or until it has been determined that the study treatment or participation is not the cause. Serious adverse events that are still ongoing at the end of the study period must be followed up to determine the final outcome. Any serious adverse event that occurs after the study period and is considered to be possibly related to the study treatment or study participation should be recorded and reported immediately.

7.3 Reporting of Serious Adverse Events and Unanticipated Problems

Investigators and the protocol sponsor must conform to the adverse event reporting timelines, formats and requirements of the various entities to which they are responsible, but at a minimum those events that must be reported are those that are:

- related to study participation,
- unexpected, and
- serious or involve risks to subjects or others
(see definitions, section 8.1).

If the report is supplied as a narrative, the minimum necessary information to be provided at the time of the initial report includes:

| | |
|---|--|
| 
• Study identifier• Study Center• Subject number• A description of the event• Date of onset | 
• Current status• Whether study treatment was discontinued• The reason why the event is classified as serious• Investigator assessment of the association between the event and study treatment |
|---|--|

Investigator reporting:

For reportable deaths, the initial submission to the UNC IRB may be made by contacting the IRB Director or Associate Director. The AE/Unanticipated Problem Form is required as a follow up to the initial submission.

Other Reportable events:

For clinical drug trials, the following events are also reportable to the UNC IRB:

- Any adverse experience that, even without detailed analysis, represents a serious unexpected adverse event that is rare in the absence of drug exposure (such as agranulocytosis, hepatic necrosis, Stevens-Johnson syndrome).
- Any adverse event that would cause the sponsor to modify the investigators brochure, protocol or informed consent form, or would prompt other action by the IRB to assure protection of human subjects.
- Information that indicates a change to the risks or potential benefits of the research, in terms of severity or frequency. For example:
 - An interim analysis indicates that participants have a lower rate of response to treatment than initially expected.
 - Safety monitoring indicates that a particular side effect is more severe, or more frequent than initially expected.
 - A paper is published from another study that shows that an arm of your research study is of no therapeutic value.
- Change in FDA safety labeling or withdrawal from marketing of a drug, device, or biologic used in a research protocol.
- Breach of confidentiality
- Change to the protocol taken without prior IRB review to eliminate apparent immediate hazard to a research participant.
- Incarceration of a participant when the research was not previously approved under Subpart C and the investigator believes it is in the best interest of the subject to remain on the study.
- Complaint of a participant when the complaint indicates unexpected risks or the complaint cannot be resolved by the research team.
- Protocol violation (meaning an accidental or unintentional deviation from the IRB approved protocol) that in the opinion of the investigator placed one or more participants at increased risk, or affects the rights or welfare of subjects.

Sponsor reporting: Notifying the FDA

The study sponsor is required to report certain study events in an expedited fashion to the FDA. These written notifications of adverse events are referred to as IND safety reports. The following describes the safety reporting requirements by timeline for reporting and associated type of event:

- ***Within 7 calendar days***

Any study event that is:

- associated with the use of the study drug
- unexpected,
- fatal or life-threatening, and

- ***Within 15 calendar days***

Any study event that is:

- associated with the use of the study drug,
- unexpected, and
- serious, but not fatal or life-threatening

-or-

- a previous adverse event that was not initially deemed reportable but is later found to fit the criteria for reporting (reporting within 15 calendar days from when event was deemed reportable).

Any finding from tests in laboratory animals that:

- suggest a significant risk for human subjects including reports of mutagenicity, teratogenicity, or carcinogenicity.

Additional reporting requirements

Sponsors are also required to identify in IND safety reports all previous reports concerning similar adverse events and to analyze the significance of the current event in light of the previous reports.

Reporting Process

Adverse events may be submitted on FDA Form 3500A or in a narrative format. If supplied as in a narrative format, the minimum information to be supplied is noted above at the beginning of section 8.3. The contact information for submitting IND safety reports is noted below:

8 Data Handling and Record Keeping

8.1 Confidentiality

Information about study subjects will be kept confidential and managed according to the requirements of the Health Insurance Portability and Accountability Act of 1996 (HIPAA). Those regulations require a signed subject authorization informing the subject of the following:

- What protected health information (PHI) will be collected from subjects in this study
- Who will have access to that information and why
- Who will use or disclose that information
- The rights of a research subject to revoke their authorization for use of their PHI.

In the event that a subject revokes authorization to collect or use PHI, the investigator, by regulation, retains the ability to use all information collected prior to the revocation of subject authorization. For subjects that have revoked authorization to collect or use PHI, attempts should be made to obtain permission to collect at least vital status (i.e. that the subject is alive) at the end of their scheduled study period.

8.2 Source Documents

Source data is all information, original records of clinical findings, observations, or other activities in a clinical trial necessary for the reconstruction and evaluation of the trial. Source data are contained in source documents. Examples of these original documents, and data records include: hospital records, clinical and office charts, laboratory notes, memoranda, subjects' diaries or evaluation checklists, pharmacy dispensing records, recorded data from automated instruments, copies or transcriptions certified after verification as being accurate and complete, microfiches, photographic negatives, microfilm or magnetic media, x-rays, subject files, and records kept at the pharmacy, at the laboratories, and at medico-technical departments involved in the clinical trial.

8.3 Case Report Forms (as applicable)

The study case report form (CRF) is the primary data collection instrument for the study. All data requested on the CRF must be recorded. All missing data must be explained. If a space on the CRF is left blank because the procedure was not done or the question was not asked, write "N/D". If the item is not applicable to the individual case, write "N/A". All entries should be printed legibly in black ink. If any entry error has been made, to correct such an error, draw a single straight line through the incorrect entry and enter the correct data above it. All such changes must be initialed and dated. DO NOT ERASE OR

WHITE OUT ERRORS. For clarification of illegible or uncertain entries, print the clarification above the item, then initial and date it.

